## **PROTOCOL SUMMARY**

**Title:** Application of 3D printing technique in small pulmonary nodule localization: A Prospective, Randomized, Controlled, Non-inferiority Trial.

**Objective:** To evaluate the accuracy and safety of template-guided lung nodule localization compared to standard computed tomography (CT)-guided localization.

**Participants:** Surgical candidates with solitary pulmonary nodule <2 cm will be approached prior to scheduled lung resection. The necessity of preoperative nodule localization would also be evaluated by the patient's operating surgeon in charge. After acquiring patients' consent to participate into the study, enrolled patients will be randomized into the CT- or template-guided group using a previously generated random table. According to priori study, each group would have a sample size of 100 participants.

[figure not shown]
**Number of site:** This is a single-center trial and all participants would be recruited in Shanghai Pulmonary Hospital.

**Description of Intervention:** The three-dimensional printed, navigational template was created to guide percutaneous lung nodule localization. Its utility has been tested in previous feasibility trial.

**Estimated Study Duration:** From 01-10-2016 to 01-07-2019.

**Estimated Time to Complete Enrollment:** From 01-10-2016 to 01-06-2019.

### Schematic of Study Design

## **LIST OF ABBREVIATIONS**

3D	three-dimensional
CT	computed tomography
GGO	ground glass nodule
VATS	video assisted thoracoscopic surgery
DLP	dose-length product
ED	effective dosage

# **1 INTRODUCTION: BACKGROUND INFORMATION AND SCIENTIFIC RATIONALE**

## **1.1 Background information**

With the widespread utilization of high resolution low-dosage CT scan in lung cancer screening, small lung nodules less than 1 cm in diameter are detected more often than ever. Biopsy resection by video-assisted thoracoscopic surgery(VATS) is an ideal option to diagnose and, at the same time, offer a curative intervention. In the dairy practice of thoracic surgery, small lung nodule resection by VATS has accounts for a large proportion.

Small-sized nodules, however, especially ground-glass opacity (GGO)-dominant nodules located deep in the lung parenchyma, are difficult to recognize during VATS. It was reported that failure of nodule localization is the most common reason leading to conversion to thoracotomy. In order to deal with this problem, there have developed many modalities to preoperatively localize the target lung nodule to facilitate nodule resection by VATS. Among those, percutaneous transthoracic lung nodule localization is the most frequently used approach because of its simplicity and independence of special equipment. Usually, the patients is taken into the CT room to receive lung nodule localization under CT guidance before the scheduled surgery. Despite its assistance in successful nodule resection by VATS, CT-guided percutaneous localization is sometimes arduous and requires many times of localizer redirection. Especially when the interventional radiologist is less experienced, it often takes many times of CT scans to accurately localize the target nodule.

With the purpose of facilitating nodule localization procedure and reduce radiation exposure, a navigational template was created using three-

dimensional (3D) printing technology and its utilization in clinical application has been preliminarily tested in previous study.

## **1.2 Rationale**

The navigational template is created based on patient's CT images. Firstly, the CT data is downloaded from Picture Archiving and Communication Systems (PACS), then imported into the computer-aided design (CAD) software to reconstruct patient's thoracic digital model. According to this digital model, the navigational template was designed to mark the puncture site and angle of the localizer prior to nodule localization. In order to achieve accurate template placement on patient's thorax, several anatomical landmarks were marked on the template to check for template alignment.

With the assistance of navigational template, the practitioner does not need to manually calculate the inserting site and angle according to the two-dimensional image, but insert the localizer according to the guidance of template.

## **1.3 Potential Risks and Benefits**

### **1.3.1 Potential Risks**

The mechanism of template-guided lung nodule localization is the same as conventional CT-guided localization. Therefore, complications related to percutaneous lung nodule localization such as pain, pulmonary hemorrhage, pneumothorax, hemoptysis and so on, likely occur. Most of these complication is non-significant and do not need special intervention.

For patient assigned to receive templated-guided nodule localization, the most worrying concern is the accuracy of lung nodule localization. Firstly, the previous feasibility trial has confirmed the precision of the navigational template, with 10.0 mm of the median localizer deviation and no occurrence of severe complications in template-guided localization. Secondly, for the sake of safety of participants in this trial, patients would receive CT scan to confirm the accuracy of the template-guided lung nodule localization after template placement but before localizer insertion.

Regarding to the concern of infection, the entire template was sterilized by UV irradiation for 30 minutes and the area adjacent to puncture point was sterilized using iodine. And the metal introducer sheath, through which the localizer was introduced, was sterilized using autoclave sterilizer. And infection of the puncture site was not found in our previous study. Additionally, as the template is made of nylon (PA3200), patients with a history of nylon allergy should not receive template-guided localization.

### **1.3.2 Potential Benefits**

Based on our priori study, the application of 3D-printed template in lung nodule localization might facilitate the process of lung nodule localization. In template-guided lung nodule localization, radiologist do not need to measure the puncture site/angle/length from the two-dimensional CT images. Instead, the template pre-specified the insertion

site and angle of the localizer. In this way, the practitioner may not need to take repeated attempts to redirecting the localizer, which leads to increased radiation exposure and high complication rate.

Therefore, patients receiving template-guided lung nodule localization would suffer less radiation exposure and lower complication rate. For the viewpoint of radiologist, the application of template significantly alleviates the challenge on practitioner and simplify the procedure of lung nodule localization. Lastly, the conventional CT-guided localization method requires the patients to stay still in one position during the whole procedure. It might be difficult for some patients, especially with obvious cough symptoms. However, in template-guided localization, the requirement about patient's position was not so strict. Patients might be more easily to cooperate in the template-guided lung nodule localization.

## **2 OBJECTIVES**

### **2.1 Study Objectives**

To evaluate the safety and accuracy of navigational template-guided method in percutaneous lung nodule localization.

### **2.2 Study Outcome**

#### **2.2.1 Primary outcome**

The primary outcome of this study is the precision of the lung nodule localization, which was specified by the localizer deviation. As the center of the nodule is the designed target, localizer deviation is measured between the center of nodule and the localizer. Regarding to measurement of the localizer deviation, because the localizer and the target nodule might be not on the same section of the CT scan, it is impossible to accurately measure the deviation from two-dimensional images.

Therefor we reconstruct the CT images upon nodule localization into three-dimensional virtual model, and precisely measure the localizer deviation in three dimensions.

### **2.2.2 Secondary outcome**

The secondary outcome includes procedural length, radiation exposure dosage and related complication rate.

In order to facilitate the process of data collection, the procedural length of nodule localization was inferred from CT scanning parameter. The time length of nodule localization is calculated from patients receiving the initial CT scan to patients receiving the last CT scan for complication evaluation. And, the radiation exposure dosage (dose-length-product) is directly collected from monitor screen after the last CT scanning. The complication related to percutaneous lung nodule localization mainly includes pneumothorax, pulmonary hemorrhage and hemoptysis during the time of waiting for surgery. The occurrence of pneumothorax and pulmonary hemorrhage is evaluated by CT scanning immediately after localizer release.

Additionally, localizer dislodgement rate and the margin distance reported on frozen analysis are also compared between patients undergoing CT-guided nodule localization and patients receiving template-guided nodule localization.

### **3 STUDY DESIGN**

The study is designed to be a prospective, randomized, non-inferiority clinical trial comparing template-guided to CT-guided peripheral small lung nodule localization. The feasibility of template-guided lung nodule localization has already been confirmed in our previous study. The study is a phase II clinical trial and further examines the safety and efficacy of template-guided lung nodule localization.

#### **3.1 Study population and groups**

The randomized, controlled trial was approved by the institutional review board of Shanghai Pulmonary Hospital. Surgical candidates with solitary pulmonary nodule less than 2cm were prospectively recruited prior to scheduled lung resection. The necessity of preoperative nodule localization was also evaluated by patient's operating surgeon in charge. After acquiring patients' consent to participate into the study, patients were randomized into CT-guided group and template-guided group respectively.

#### **3.2 Sample Size Calculation**

The study was designed to confirm the non-inferiority of template-guided lung nodule localization compared to CT-guided lung nodule localization in terms of localization accuracy. And the accuracy of lung nodule localization was quantified by the localizer deviation between the localization and the center of the target nodule.

The expected difference of localizer deviation between CT- and template-guided group was 3.5mm according to priori study. Deviation of 5mm is set as non-inferiority margin. We needed to randomize 140 patients (70 each group) to give 90% power with one-sided alpha of 0.05. To allow for some dropouts, inclusion of 100 patients per group is planned.

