### **3.5 Statistical Analysis**

To decide whether the localization accuracy, radiation exposure and complication rate in the two groups are significantly different, three tests are used: 1) independent samples  $t$  tests for continuous variables that were normally distributed; 2)  $X^2$  tests for categorical variables, and 3.) Mann-Whitney U test for continuous variables that were not normally distributed.

Because of the possibility of patients withdraw, intention-to-treatment (ITT) analysis and efficacy analysis are both performed. ITT analysis is conducted for participants who received lung nodule localization and subsequent surgery. Efficacy analysis is only performed for patients who received lung nodule localization according to their assignment. All statistical analyses are two-tailed with a significance level of 0.05.

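### Sample size is computed at one-sided 0.05 but all analyses are set at two-tailed 0.05; at that level, and if 70 per group is right for its inputs, power at 70 is about 83%, not 90%

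*Combined protocol and SAP*

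**What the plan says.** Section 3.2 (Sample Size Calculation) gives a non-inferiority calculation for localizer deviation. Its inputs are an expected difference ("The expected difference of localizer deviation between CT- and template-guided group was 3.5mm according to priori study") and a margin ("Deviation of 5mm is set as non-inferiority margin"). Its result is "We needed to randomize 140 patients (70 each group) to give 90% power with one-sided alpha of 0.05". It states no SD and does not say which group is expected to deviate more. It then adds: "To allow for some dropouts, inclusion of 100 patients per group is planned".

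Section 3.5 (Statistical Analysis) opens with "To decide whether the localization accuracy, radiation exposure and complication rate in the two groups are significantly different, three tests are used" and names the independent-samples t test, the chi-squared test and the Mann-Whitney U test. It ends with "All statistical analyses are two-tailed with a significance level of 0.05". Localization accuracy, the primary outcome in section 2.2.1, is the first item in its list. The section mentions neither the 5 mm margin nor a confidence interval, and exempts no analysis from the two-tailed level.

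**The concern.** A non-inferiority conclusion rests on one direction only: the template must not be worse than CT guidance by as much as 5 mm. A two-tailed 0.05 level places 0.025 in that direction, half of the 0.05 used to size the trial. A power figure holds only at the level at which the test is run, so the 90% and the 70 per group do not carry over to section 3.5.

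Two things are at stake. First, whether a 90% or a 95% two-sided interval is set against 5 mm can change the trial's conclusion when the result is near the margin, so the choice must be fixed before the data are seen. Second, section 3.2 treats 70 as sufficient and the other 30 per group as cover for dropouts. At the section 3.5 level, part of that cover is needed simply to reach 90% power.

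Some loss is to be expected. Section 4.6 removes patients who withdraw after randomization and those whose resection is cancelled. Section 3.5 limits the set it calls intention-to-treat to patients who had both localization and surgery. The efficacy set is limited further to those localized as assigned, and section 5.2 moves some template patients to CT guidance.

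**Working it through.** **Inputs (section 3.2 unless noted).** n = 70 per group, 1:1; power 90%; alpha 0.05 one-sided; margin 5 mm; expected difference 3.5 mm, direction not stated; 100 per group planned. From section 3.5: 0.05 two-tailed, that is 0.025 in the non-inferiority direction. SD: not stated.

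**Step 1. Can the plan's 70 be reproduced?** The usual formula is n = 2 × [SD × (z_alpha + z_beta) / delta]², where delta is the distance from the true difference to the margin. Without an SD, n cannot be derived. Solving backwards, SD = delta × √(70/2) / (1.645 + 1.282) = delta × 5.916 / 2.926:

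- Template expected 3.5 mm worse: delta = 5 − 3.5 = 1.5, SD = 3.03 mm.
- No true difference: delta = 5, SD = 10.1 mm.
- Template expected 3.5 mm better: delta = 5 + 3.5 = 8.5, SD = 17.2 mm.

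Round SDs of 3 mm (first reading) and 10 mm (second) each give 69 per group, so 70 is attainable under more than one reading. It is not confirmed under any of them.

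**Step 2. What the stated figures fix.** If 70 per group does give 90% power at one-sided 0.05, the standardized distance to the margin at n = 70 is

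delta × √(n/2) / SD = 1.645 + 1.282 = 2.926,

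whatever the SD and whatever the direction of the 3.5 mm. The steps below use only this value.

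**Step 3. Power at 70 per group at the section 3.5 level.**

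Phi(2.926 − 1.960) = Phi(0.966) = 83.3%.

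With the noncentral t distribution throughout (effect re-solved to give 90% at one-sided 0.05), the figure is 83.2%.

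**Step 4. Size needed for 90% at that level.**

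n = 70 × [(1.960 + 1.282) / (1.645 + 1.282)]² = 70 × (3.242 / 2.926)² = 85.9, so 86 per group (172 in total).

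Power is 89.7% at 85 and 90.0% at 86. The noncentral t gives 87.

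**Step 5. What the planned 100 per group delivers.** The standardized distance becomes 2.926 × √(100/70) = 3.498, and power is Phi(3.498 − 1.960) = 93.8%.

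**Step 6. The cushion.** Going from 70 to 86 uses 16 of the 30 extra patients per group, 16/30 = 53%. The loss from 100 that still leaves 90% power is (100 − 86)/100 = 14%. At one-sided 0.05 the corresponding loss is (100 − 70)/100 = 30%.

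| Evaluable per group | Power, one-sided 0.05 | Power, two-tailed 0.05 |
|---|---|---|
| 70 | 90% | 83.3% |
| 86 | above 90% | 90.0% |
| 100 | 96.8% | 93.8% |

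**Step 7. How far the result leans on 70 being right.** As an illustration only, assume the template is expected to be 3.5 mm worse and the SD is 4 mm rather than 3.03 mm. At 70 per group the standardized distance is 1.5 × 5.916 / 4 = 2.22. Power is then Phi(2.22 − 1.645) = 72% at one-sided 0.05 and Phi(2.22 − 1.960) = 60% at 0.025. With 86 per group it is 69% at 0.025. The 83% and the 86 are therefore conditional figures.

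**The case against.** The strongest reply is that the closing sentence of section 3.5 belongs to the difference tests listed above it, while section 3.2 sets the non-inferiority level separately and explicitly. On that view the 90% is uncontradicted. The sentence, however, covers all analyses, and localization accuracy is among the outcomes section 3.5 says it will test. Nothing in either section reserves one-sided 0.05 for the primary comparison. If that was the intention, the two sections still need reconciling.

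A second reply is that the 83% describes an analysis the plan does not contain, since section 3.5 has no comparison with 5 mm. This stands as a condition on the figure. The missing margin comparison is a separate defect, and adding it would not settle which alpha applies. It does mean that section 3.2 cannot be corrected alone.

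A third reply is that 70 cannot be verified without an SD. This also stands: the loss of power from 90% to 83% follows from the stated n, alpha and power, but only if those three are consistent with each other.

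A reader might infer two stronger things. One is that the trial is underpowered. The documents do not support that: 100 per group gives about 94% on the same assumptions, and nothing indicates that losses will exceed 14%. The other is that the sponsor counts on losing 30% while keeping 90% power. Section 3.2 refers only to some dropouts and states no rate; the 30 per group is simply the gap between 70 and 100.

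**Conclusion.** The stated power is wrong as written at the level the plan sets for its analyses. On two assumptions, that 70 per group is correct for its own inputs and that the upper limit of the two-sided 95% interval is compared with 5 mm, the shortfall at 70 per group is about 7 percentage points. The tolerable loss from 100 per group is roughly halved. The result does not depend on the direction of the 3.5 mm difference, nor on the SD once 70 is accepted. The practical consequence is a smaller safety allowance and an unsettled decision rule, not a demonstrated lack of power at the planned enrolment.

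**What to change.** Use one alpha in sections 3.2 and 3.5.

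- **Section 3.5:** state that non-inferiority is concluded if the upper limit of the two-sided 95% confidence interval for the difference in mean localizer deviation (template minus CT) is below 5 mm. The listed difference tests do not supply this rule, and the Mann-Whitney test does not give an interval for a mean difference.
- **Section 3.2:** restate the calculation at that level, giving the SD and the direction of the 3.5 mm difference. If the SD reproduces 70 at one-sided 0.05, the text can read: about 83% power with 70 evaluable per group, 90% with about 86 (87 by the t distribution), and 90% kept at 100 per group with losses up to about 14%. If the SD does not reproduce 70, recompute all of these figures before entering them.

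If the sponsor intends one-sided 0.05 for the primary comparison, section 3.5 must say so as an explicit exception and name the matching 90% two-sided interval.

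The cost is wording in two sections. Enrolment stays at 100 per group unless the recomputation shows otherwise. The downside is a slightly less favourable stated power and a smaller stated allowance for losses.

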### **3.3 Interim Analysis**

An interim-analysis is performed on the primary and secondary outcomes when 40% of patients have been randomized. The interim-analysis is performed by an independent statistician, blinded for the treatment allocation. The data monitoring committee will have unblinded access to all data and will discuss the results of the interim-analysis in a joint meeting, and report to the ethics committee. Based on the results of interim-analysis, principal investigator decides whether the trial continues or not. The trial will be ended if the localizer deviation is significantly larger in template-guided lung nodule localization than CT-guided localization, and no benefit is obtained for patients undergoing template-guided lung nodule localization. Otherwise, the trial will be continued.

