### **4.3 Treatment Assignment Procedures**

In order to randomly assign the participants to the two groups, a randomization list with 200 numbers was created using blocked randomization with a block size of 10. The 200 random numbers are each placed in sealed envelopes which are marked with sequential number at the cover.

Patients with scheduled lung resection are evaluated by research assistants. If the above criteria are met and patient's consent to participation has also been acquired, then the patient's information is sent to a person who is not involved with the trial by calling. Then, the accorded envelop is opened to assign the patient to template- or CT-guided localization group.

Because of the intrinsic property of the trial, no masking procedure is performed. After assignment, if the patient is allocated to template-guided lung nodule localization, research assistant needs to download the patients CT data from Picture Archiving and Communication Systems. The planned localization route is marked on CT images by patient's surgeon, then the CT data is emailed to designers for template design and printing. Because it takes about 6-8 hours for template production, all enrolled patents have to give consent to participate at least one day before the scheduled surgery.

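### Section 3.3 leaves the interim stop-or-continue decision to the principal investigator of an unmasked trial, which implies access to between-arm results that the existing data monitoring committee makes unnecessary

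*Combined protocol and SAP*

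**What the plan says.** Section 3.3 of the combined protocol and SAP plans one interim analysis of the primary and secondary outcomes at 40% randomized. Three parties have a role.

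- An independent statistician, blinded to allocation, runs the analysis.
- A committee reviews it: "The data monitoring committee will have unblinded access to all data". It discusses the results in a joint meeting, whose participants are not named, "and report to the ethics committee".
- The principal investigator decides: "Based on the results of interim-analysis, principal investigator decides whether the trial continues or not".

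The trial stops if localizer deviation is significantly larger with the template than with CT guidance "and no benefit is obtained for patients undergoing template-guided lung nodule localization. Otherwise, the trial will be continued". No recommendation from the committee to the investigator is described. Section 4.3 says that "no masking procedure is performed".

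**The concern.** A person who knows which arm is ahead, and who is still responsible for the conduct of the trial, can influence what follows, even unintentionally. A data monitoring committee exists to keep that knowledge away from those who run the study. Section 3.3 sets up such a committee but gives it no recommending role, and passes the decision to the investigator.

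Here the primary outcome is partly a product of operator effort. Section 5 has the same practitioner perform every localization in both arms. Section 5.1 lets that practitioner repeat scans and redirect in the CT arm until accuracy is judged adequate. If awareness of the interim comparison reached the procedure room, effort could shift differently in the two arms, and the final non-inferiority comparison would mix data from before and after that shift.

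**Working it through.** The question is mainly one of reading the text. The arithmetic shows only how much of the trial is exposed.

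**Step 1. Does the decision need results by arm?** The first stopping condition is directional: the template must be worse than CT guidance. The second asks about benefit to template patients. A comparison of coded groups A and B, which a blinded statistician could produce, cannot settle either condition until the codes are linked to the arms. The text gives unblinded access only to the committee, yet the investigator must decide on the results. Either the investigator receives results by arm, or the investigator cannot apply the rule. The first reading is the natural one, but it is an inference.

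**Step 2. Is that access needed?** No. The committee already has the unblinded data, already discusses the interim results and already reports to the ethics committee. It can apply the same rule.

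**Step 3. How much of the trial follows the interim?**

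- Planned recruitment is 100 per group, so 200 (section 3.2).
- Interim: 0.40 × 200 = 80 randomized.
- Remaining: 200 − 80 = 120, and 120/200 = 60%.
- Duration at the stated rate of about 10 per month (section 3.4): 120/10 = 12 months.
- Duration if 200 patients are spread over the 32-month enrolment window in the Protocol Summary: 200/32 = 6.25 per month, and 120/6.25 = about 19 months.
- If the 40% were counted on the 140 required patients: 0.40 × 140 = 56, leaving 144 of 200 (72%).

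**Step 4. Is there room for conduct to affect the outcome?** Section 5.1 treats any deviation up to 2 cm as accurate enough. The non-inferiority margin in section 3.2 is 5 mm. The accepted range is thus 20/5 = 4 times the margin, and how far to refine within it is left to judgement in the CT arm. In the template arm, section 5.2 proceeds if the first scan shows a deviation under 2 cm and otherwise switches to CT guidance. The discretion therefore differs between arms. This shows that there is room for an effect, not that one occurs.

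**Step 5. Can a bias be sized?** If conduct after the interim shifted the between-arm difference by d mm in the remaining 60%, the pooled difference would move by 0.6 × d, assuming equal arms and no withdrawals. The documents give no basis for the size or direction of d. They also state no standard deviation, so even an assumed d could not be turned into an error rate without further assumptions.

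**The case against.** The strongest reply has four parts.

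*The investigator's access is inferred.* This is correct. Section 3.3 grants unblinded access to the committee only. But a decision based on the results, under a rule that names the arms, is hard to read otherwise. If it was not intended, the sentence still needs rewording.

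*The practitioner is unmasked anyway and sees cases accumulate in both arms; the investigator may be someone else.* Both points stand, and they limit how much one formal look adds. A formal comparison with a significance test is still more than case-by-case impression, and withholding it costs nothing.

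*Other safeguards limit the damage.* Deviation is calculated in CAD software (section 6.1), which restrains measurement bias but not conduct. The check before insertion in section 5.2 and the report to the ethics committee protect patients. The issue is therefore operational bias, not patient harm. A reader might also infer that an informed surgeon could steer patients between arms through the eligibility judgement. The documents do not support this: under section 4.3 that judgement precedes allocation, which is by sealed envelope through a person outside the trial.

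*The stopping rule itself is adequate.* A reader might infer that the benefit condition has no content, that the accuracy test is ambiguous between zero and the margin, or that it is open whether a benefit outweighs a large accuracy loss. None of these holds as an error.

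- Section 1.3.2 names less radiation and fewer complications as the expected benefits. Section 2.2.2 lists the outcomes: "The secondary outcome includes procedural length, radiation exposure dosage and related complication rate", and "localizer dislodgement rate and the margin distance reported on frozen analysis are also compared". Section 3.5 names radiation exposure and complication rate for testing, two-sided at 0.05. Only a cross-reference from section 3.3 is missing.
- Significantly larger than CT guidance is plainly a test against zero. The statement "Deviation of 5mm is set as non-inferiority margin" belongs to the final non-inferiority comparison.
- The two conditions are joined by 'and', and the trial otherwise continues. A benefit therefore does prevent stopping. Paired with the benefit condition, a test against zero is a defensible benefit-risk rule.

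**Conclusion.** The point holds as a matter of governance. In an unmasked trial, section 3.3 gives the continuation decision to the principal investigator on results that, by the wording of the rule, must be comparative, although a committee able to apply the rule is already in place. The exposure is 120 of 200 patients (60%) if the 40% is counted on planned recruitment, over 12 to 19 months depending on the enrolment rate.

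A reader might infer that the final result will be biased by a calculable amount. The documents do not support that: they give no shift, no standard deviation and no statement of whether the investigator is also the practitioner. Nor is the final type I error affected by the interim rule, which allows no early claim of non-inferiority.

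The conclusion rests on one inference, that the investigator sees results by arm, so confidence is medium. The change should be made because it lowers a recognised risk for the price of a sentence.

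**What to change.** Replace the quoted sentence in section 3.3 with:

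> The data monitoring committee applies the stopping rule to the comparative results and recommends stopping or continuing to the ethics committee and the principal investigator; the principal investigator acts on that recommendation and does not receive comparative results before the trial ends.

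This keeps a named person who acts, gives the committee the role it lacks, and leaves the stopping rule unchanged.

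As a minor clarification, not a separate error, let section 3.3 point from 'benefit' to the outcomes already named in sections 1.3.2, 2.2.2 and 3.5.

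Cost: protocol wording only, with review by the institutional review board as section 7.2 requires for any amendment. No new staff, no more patients and no change in the final alpha. The downside is that the investigator must rely on the committee's judgement without seeing the figures behind it.

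### An excess of complications alone does not meet the written interim stop rule in section 3.3, and that rule conflicts with the sentence leaving the decision to the principal investigator

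*Combined protocol and SAP*

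**What the plan says.** The objective in section 2.1 puts safety beside accuracy: "To evaluate the safety and accuracy of navigational template-guided method in percutaneous lung nodule localization". Section 2.2.2 makes complications a secondary outcome: "The secondary outcome includes procedural length, radiation exposure dosage and related complication rate". Section 3.3 brings them into the interim look: "An interim-analysis is performed on the primary and secondary outcomes when 40% of patients have been randomized".

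Section 3.3 then says three things about what follows the look.

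- **Review.** "The data monitoring committee will have unblinded access to all data and will discuss the results of the interim-analysis in a joint meeting". The committee also reports to the ethics committee.
- **Decision.** "Based on the results of interim-analysis, principal investigator decides whether the trial continues or not".
- **Rule.** The first condition concerns accuracy: "The trial will be ended if the localizer deviation is significantly larger in template-guided lung nodule localization than CT-guided localization". The same sentence joins to it a second condition, which must hold as well: "and no benefit is obtained for patients undergoing template-guided lung nodule localization". The closing sentence covers every other result: "Otherwise, the trial will be continued".

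Outside section 3.3, section 8 has the principal investigator review adverse events and unanticipated problems. Sections 5.2 and 6.4 describe how complications are observed and recorded. None of these gives a criterion for pausing or ending the trial.

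**The concern.** The look produces a comparison of complications by arm, and the committee sees it unblinded, but the written rule is built on accuracy. Its two conditions are joined by *and*, and its last sentence sends every other result to continuation. A template arm with clearly more pneumothorax or hemorrhage, and deviation no larger than in the CT-guided arm, falls on the continue side.

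At stake is the protection of patients randomized after the look, in a trial with safety as an objective. If complications pointed against the template, those responsible would find one sentence that leaves the decision open and another that directs them to continue, with no agreed standard for choosing between them. The trial is unmasked (section 4.3), so a standard set only after the results are known would be hard to defend.

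**Working it through.** **1. The rule as logic.** Let A be significantly larger deviation with the template, and B be no benefit for template patients. Section 3.3 stops on A and B together and continues otherwise.

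| A: deviation larger | B: no benefit | Written outcome |
|---|---|---|
| yes | yes | stop |
| yes | no | continue |
| no | yes | continue |
| no | no | continue |

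**2. Where complications enter.** Section 1.3.2 lists lower radiation exposure and fewer complications as expected benefits of the template. A poor complication result can therefore help to make B true. In row 3, B is true and the trial still continues. In row 2, a gain elsewhere, such as lower radiation exposure, could make B false despite more complications, depending on how benefit is read.

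**3. Size of the look.** Section 3.2 plans 100 per group, so 0.40 × 200 = 80 patients, or 40 per arm. If 40% of the calculated 140 is meant, it is 0.40 × 140 = 56, or 28 per arm.

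**4. Illustration.** The documents give no complication rates, so these counts are assumptions. Take 2/40 (5%) CT-guided and 10/40 (25%) template-guided.

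- Pooled rate: 12/80 = 0.15.
- Standard error under no difference: √(0.15 × 0.85 × 2/40) = 0.0798.
- z = 0.20/0.0798 = 2.50, so Pearson chi-square p = 0.012. Fisher's exact test gives p = 0.025.
- 95% Wald interval: 0.20 ± 1.96 × √(0.05 × 0.95/40 + 0.25 × 0.75/40) = 0.20 ± 0.15, about 5 to 35 percentage points.

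Other assumed counts give the same reading: 4/40 versus 16/40 has chi-square p = 0.002, and 8/40 versus 20/40 has p = 0.005. In each case, if deviation is not significantly larger, the written outcome is to continue.

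**5. How often the rule can be met.** Suppose true deviations are equal and the two-sided 0.05 level of section 3.5 is used at the look (section 3.3 sets no interim level). Then A occurs with probability 0.05/2 = 0.025. Stopping needs A, so the rule is met at most 2.5% of the time, whatever the true complication rates.

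**6. What the look could detect.** Approximate power of a two-sided 0.05 comparison of complication rates, all rates assumed:

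| CT-guided vs template-guided | 40 per arm | 28 per arm |
|---|---|---|
| 10% vs 20% | 0.24 | 0.18 |
| 10% vs 30% | 0.61 | 0.46 |
| 20% vs 50% | 0.82 | 0.66 |

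The look can reveal a large excess but will often miss a moderate one.

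**The case against.** The best counterargument is in section 3.3 itself. The principal investigator decides on the interim results, which include complications, and the committee reports to the ethics committee. A reader might infer from the closing sentence that harm could never stop the trial, or that the committee's review leads nowhere. The documents do not support either inference: there is a decision-maker who has the complication data, and the results go to a body beyond the trial team. Nor does the rule ignore complications altogether, since they can bear on the no-benefit condition.

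It would also be wrong to treat the adverse-event review in section 8 as the only other safety oversight. Template patients have a CT check before hookwire insertion (sections 1.3.1 and 5.2). At least two research assistants attend each procedure, with CT after the localizer is deployed (section 6.4.1), and nurses monitor patients until surgery (section 6.4.2). These protect the individual patient. They do not say when an imbalance between arms should halt randomization.

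Section 1.3.1 also expects most complications to be minor and the mechanism to match that of CT guidance. That is a reason to weigh severity in any criterion, but it does not supply one.

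What remains is that no section states a harm criterion or a power to stop for harm, and the discretion in section 3.3 is followed directly by a sentence directing continuation in every case but one.

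**Conclusion.** The point holds as a defect in the written rule: complications alone cannot satisfy it, and section 3.3 does not reconcile the rule with the principal investigator's discretion. This rests on the text and needs no assumed rate. The counts above only show that a nominally significant excess at 40 per arm would still be directed to continuation. They are not evidence about the template, and a reader should not infer that it causes more complications; even in the illustration, one unadjusted comparison leaves an interval of about 5 to 35 points.

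The change should be made. It concerns participant protection and does not invalidate the primary analysis. Settling the accuracy margin, the meaning of benefit or the decision-maker would not by itself supply a harm criterion.

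**What to change.** In section 3.3, replace the closing sentence with text that does three things.

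1. **Add a safety limb.** At the 40% look the data monitoring committee reviews the section 6.4 complications by arm, and may recommend a pause or stop on complications alone, whatever the deviation or benefit result. The committee and sponsor fix the criterion in writing before any unblinded data are seen, including how minor and serious events count. Its content is theirs to choose.
2. **Reconcile the decision.** State whether the recommendation binds the principal investigator or informs the decision, so that the discretion and the continuation rule no longer conflict.
3. **Restate the default.** The trial continues only if neither the accuracy limb nor the safety limb is met.

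The cost is a few sentences and one short document fixing the criterion. No new data are needed, because complications are already analysed at this look. The drawback is a slightly higher chance of stopping early on a chance imbalance. A stop for harm alone gives no added opportunity to claim non-inferiority, so it does not raise the false-positive rate of that claim.
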